Human IFN- γ ELISA: We will collect 5 ml of peripheral blood using citrate, EDTA, or heparin as anticoagulant from the patients before and 2 weeks after treatment. Plasma will be collected by centrifuging the blood for 10 minutes at 1000 x g within 20 minutes of collection. The plasma will be stored at $\leq 20^{\circ}\text{C}$ or shipped on dry ice. We will analyze the patient plasma samples for in vitro T-cell function by ELISPOT assay using tumor specific antigens. A positive interferon gamma (IFN- γ) response to a common antigen (such as whole influenza virus or EBV) will be used as a control. The results will be correlated to the skin changes and clinical outcome of the patients.

9.0 PATIENT REGISTRATION:

All patients will be registered through the Clinical Trials Office at Montefiore Medical Center ([contact]) Monday through Friday 9:00am – 5:00pm Eastern Standard Time. Eligibility Checklist and Registration Form with supporting documentation, and the signed Patient Consent Form must be emailed to the clinical trials office at Montefiore Medical Center, [contact] , at the time of registration and prior to patient treatment. Please copy the Montefiore Study and Regulatory Coordinator on this email, as well as the Principal Investigator at Montefiore. E-mail addresses are available at the cover sheet of this protocol document.

[figure not shown]
At the time of registration, all eligibility criteria must be checked. Patients must meet all of the eligibility requirements listed in Appendix B (Eligibility Checklist) (Section 3.0). Patients must not start protocol treatment prior to registration.

It is the treating physician's responsibility to review all data submitted to the Clinical Trials Office for accuracy and completeness and he/she must sign the off study form.

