18.1 Study Design/Analytic Plan

- The primary statistical objectives of this single arm open label phase II study to obtain preliminary estimates of the rate of mediastinal nodal clearance and the rate of complete pathological response in patients with stage III NSCLC with EGFR mutations who received neoadjuvant erlotinib and had surgical resection. Historical data from the neoadjuvant studies with chemotherapy or chemoradiotherapy in resectable NSCLC patients had mediastinal nodal clearance between 15-40%. We hypothesize that patients with stage III EGFR mutated NSCLC treated with neoadjuvant erlotinib therapy must have comparable rates of mediastinal down staging and complete path response for this strategy to evaluate further in this subset of NSCLC patients.
- The mediastinal nodal clearance is defined as pathologically negative N2 disease in the final surgical resection specimen or mediastinoscopy. This can be objectively measured and has been confirmed as the best predictor of long term survival in patients with stage III NSCLC treated with neoadjuvant therapy and had surgical resection.
- Secondary objectives are to estimate objective overall response rate [ORR, i.e., complete response (CR) + partial response (PR)], disease control rate (CR+PR+SD), the surgical resection rate, the progression free (PFS) and overall survival (OS), and the safety of neoadjuvant erlotinib followed by surgical resection in patients with stage III EGFR mutated NSCLC.
- PFS is defined as the time from randomization until documented tumor progression or death from any cause. PFS is censored at the date of the last follow-up visit for patients who are still alive and who have not progressed. OS is defined as the time from the date of randomization to date of death due to any cause.
- Response rates will be summarized by computing proportions and corresponding 95% confidence intervals. Time to event endpoints will be analyzed using standard survival analytic methods, including the Kaplan-Meier approach for estimating the survival distributions. Median time to event and 95% confidence intervals will be estimated from the Kaplan-Meier curves. All primary and secondary analyses will be based on the intent-to-treat principle.

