18.3 Randomization and Stratification

This will be a single arm phase II study and no randomization or stratifications will be involved

18.4 Evaluation of toxicity.

All patients will be evaluated for toxicity from the time of their first treatment with erlotinib. All of the surgical procedures in the protocol are the usual standard of care in treating patients with stage III NSCLC. However, we will monitor and record all postoperative complications. Certain postoperative complications are expected after lung resection and/or mediastinoscopy. We will particularly monitor 30 day mortality, development of bronchopulmonary fistula or prolonged wound healing. If the rate of these is more than what is expected as standard of care, the regulatory authorities will be reported and the trial will be suspended for toxicity.

18.5 Evaluation of response.

All patients who meet the eligibility criteria and have received at least one dose of treatment will be assessed for response to treatment.

19.0 REFERENCES:

5. Non-small Cell Lung Cancer Collaborative Group. 1995. Chemotherapy in non-small cell lung cancer: a meta-analysis using updated data on individual patients from 52 randomized clinical trials. *Br Med J* 311(7010):899-909.

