The following minimum required laboratory data must be done within 14 days of treatment.			
Absolute neutrophil count $\geq 1,500$ cells/ul: Numerical value _____ Date of test _____			
Platelets $\geq 100,000$ cells/ul Numerical value _____ Date of test _____			
Hemoglobin ≥ 9.0 g/dl Numerical value _____ Date of test _____			
Serum creatinine ≤ 1.5 x ULN Numerical value _____ Institution ULN _____ Date of test _____			

Eligibility Criteria: The answers to the following questions must be **YES NO N/A**
'yes' in order for the patient to be eligible. N/A should only be
answered if description within question allows.

INCLUSION CRITERIA

Total Bilirubin < 2.0 x institutional upper limits of normal
 
Numerical value _____
 
Institution ULN _____ Date of test _____
			

AST and ALT \leq 2.5 x the ULN
 
Numerical value _____
 
Institution ULN _____ Date of test _____
			

For women of Child-bearing potential: A negative serum or urine pregnancy test (sensitivity \leq 25IU HCG/L) within 72 hours prior to the start of study drug administration
 
Beta HCG: State results: _____ Date of test _____ State date of Rx _____
			

Persons of reproductive potential must agree to use and utilize an adequate method of contraception throughout treatment and for at least 4 weeks after study drug is stopped. Prior to study enrollment, men and women of childbearing potential must be advised of the importance of avoiding pregnancy during trial participation and the potential risk factors for an unintentional pregnancy.
 
Does patient agree to use adequate method of contraception?
			

Ability to take oral medication
			

Patient signed the study specific informed consent. (The patient must be aware of the neoplastic nature of his/her disease and must willingly consent after being informed of the procedure to be followed, the experimental nature of the therapy, alternatives, potential benefits, side effects, risks, and discomforts.)
 
Date signed: _____
 
Version: _____
 
Expiration date of ICF: _____
			

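### PFS and OS are timed from a randomization that this single-arm trial does not have; PFS also lacks a scan start date and is censored at a visit rather than a tumour assessment

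*Combined protocol and SAP*

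**What the plan says.** Section 18.1 defines both time-to-event endpoints from the same event: "PFS is defined as the time from randomization until documented tumor progression or death from any cause", and "OS is defined as the time from the date of randomization to date of death due to any cause". Section 18.3 then says: "This will be a single arm phase II study and no randomization or stratifications will be involved".

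Two other dates appear in the protocol, but neither is tied to PFS or OS. Section 9.0 makes registration a separate, earlier step: "Patients must not start protocol treatment prior to registration". Section 18.4 uses first dose, for safety only: "All patients will be evaluated for toxicity from the time of their first treatment with erlotinib".

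On censoring, Section 18.1 says: "PFS is censored at the date of the last follow-up visit for patients who are still alive and who have not progressed". The median and its 95% confidence interval come from the Kaplan-Meier curve. On the analysis set it says: "All primary and secondary analyses will be based on the intent-to-treat principle".

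The Section 6.1 calendar puts follow-up imaging at six-month intervals in the first year and yearly after that, to five years. It does not say from which date the intervals run. A footnote adds follow-up for survival and recurrence, three-monthly in the first year and six-monthly later.

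**The concern.** A time-to-event endpoint needs an origin that exists for every patient. Here it exists for none. The analyst must choose one, and so may each of the several centres named in Section 18.2. A choice made after data are in hand is open to challenge even when it is harmless.

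The second issue is separate, and naming an origin does not cure it. PFS events are dated when progression is documented, which is at or after the time it occurs. With scans 6 and then 12 months apart, the delay can be material. Censoring at the last visit also credits a patient with progression-free time after the last tumour assessment. The Section 2.0 background sets median PFS of 12-13 months for chemoradiation beside 10-13 months for erlotinib in stage IV disease, so a reader is likely to place this trial's median next to those figures. A shift of one to three months is as wide as those ranges.

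**Working it through.** **The plan's own figures.** The plan gives no assumed median, event count or power for PFS or OS, so there is nothing to reproduce for them. The two-stage design in Section 18.2 (3/19, then 12/55; 15% against 30%) does reproduce: power 0.8006, type I error 0.0477, early stopping 0.684 and 0.133. It uses neither PFS nor OS.

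**Candidate origins** (30.44 days per month).
- Registration or first dose. Appendix B says "The following minimum required laboratory data must be done within 14 days of treatment". Eligibility laboratory results precede registration, so if this window governs, the gap is at most 14 / 30.44 = 0.46 month. Section 3.1 instead counts the blood count back from registration, and footnote A of Section 6.1 counts laboratory tests back from study entry. Neither limits the time from registration to first dose. Section 7.1 wants baseline tumour evaluations no more than 4 weeks before treatment. That would cap the gap at 28 / 30.44 = 0.92 month, provided the eligibility scan serves as baseline and is not repeated.
- Surgery. Day 57 is 56 days after Day 1, and Section 4.2 places surgery 4-6 weeks after restaging: (56 + 28) / 30.44 = 2.8 to (56 + 42) / 30.44 = 3.2 months. This origin does not exist for unresected patients and cannot be squared with intent-to-treat.

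**Where the scan schedule might start.** The nearest natural dates are the Section 14.0 visits.
- Without surgery, taking the Post-Treatment Visit as Day 57 (an assumption): (56 + 30) / 30.44 = 2.8 months after Day 1.
- With surgery: (84 + 30) / 30.44 = 3.7 to (98 + 30) / 30.44 = 4.2 months.

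**Simulated effect on the Kaplan-Meier median.** From the documents: 55 patients, accrual of 30 months (middle of 24-36), 12 further months of follow-up, scans at Day 57 and at 6, 12, 24 and 36 months from the start dates above, and visits 3-monthly then 6-monthly. Assumed, not in the documents: exponential PFS, half of patients resected, 15-month median survival after progression, and a stated share of progressions found at the next visit with the rest found at the next scan. True medians of 10.4 and 13.1 months are figures in Section 2.0; 12 is a mid-range value.

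| True median (months) | Typical KM median, 50-100% found at visits | Shift | Typical KM median, none found at visits | Shift |
|---|---|---|---|---|
| 10.4 | 11.8-12.8 | 1.4-2.4 | 14.8 | 4.4 |
| 12 | 13.1-14.8 | 1.1-2.8 | 14.8 | 2.8 |
| 13.1 | 14.8 | 1.7 | 15.8 | 2.7 |

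A control with exact progression dates returns 10.4, 12.1 and 13.2, so the shift comes from the schedule and not from the estimator.

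**How far the size moves.**
- True median 15.7 months (the erlotinib-alone figure in Section 2.0), same model: about 0.5 month. A variant with other scan start dates and detection shares, comparing observed and true medians within each trial, gives 1.3-7.7 months.
- Scans counted from entry, a less natural reading: typical medians 12.0, 12.0-14.0 and 18.0 for true 10.4, 12 and 13.1. The shift can be zero when the true median of 12 coincides with a scan, and is about 5 to 6 months at 13.1.

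**What the remedies do.** Censoring at the last scan leaves the typical median unchanged in most cells, and at most 1.6 months lower. An interval-censored Weibull model reads 0.8 to 1.5 months below the truth in the main cells.

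**The case against.** The origin is a wording slip. The two realistic substitutes probably differ by weeks, and no decision depends on them. That limits the impact, but the definitions still cannot be followed as written.

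The case against the second part is stronger, and most of it stands.
- The endpoint is time to documented progression, and Kaplan-Meier on documented dates estimates exactly that. The shift is relative to a latent progression time that the plan does not claim to estimate.
- The three- and six-monthly recurrence visits reduce the delay.
- The model has deaths only after progression. If 20% of patients die without prior progression (an assumption), the shift falls in some cells (2.4 to 1.5, 1.8 to 1.0) and is unchanged in others.
- The 95% interval for the median is typically 7 to 12 months wide, so the shift is small beside sampling error.
- The proposed censoring rule barely moves the median.

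A reader might infer that this plan overstates median PFS by 1 to 3 months. The documents do not support that. They give no PFS assumption for this trial, no share of progressions found at visits and no scan start date, and the result depends on where the true median falls on the scan grid. A reader might also infer that comparison with the cited PFS figures is biased. No formal comparison is planned, and the scan schedules behind those figures are not given, so they may carry a similar shift.

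**Conclusion.** Certain, with no assumption needed: PFS and OS have an origin that does not occur in this trial, and nothing else in the documents supplies one. Registration and first dose differ by at most 0.46 month if the Appendix B window applies; the other laboratory windows give no limit.

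Conditional: the Kaplan-Meier PFS median tends to be late. Roughly 1 to 3 months is reasonable for true medians of 10 to 13 months when at least half of progressions are found at visits. Other scan start dates, detection shares or true medians take it from near zero to 5-6 months or more. The direction is well founded; the size is not a property of the plan.

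Impact is low. Only secondary endpoints are touched, and OS (labelled exploratory in Section 1.2) only through its origin. The nodal-clearance endpoint, N = 55 and the stopping and final decision limits are unchanged.

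**What to change.** 1. Define PFS and OS from the date of registration. This suits the intent-to-treat sentence, because a patient who is registered but never dosed still has a time zero.
2. Censor PFS at the last adequate tumour assessment.
3. State the date from which the follow-up scan schedule runs, separately for patients with and without surgery.
4. Keep the Kaplan-Meier median, and say beside it that its precision is limited by the 6- and 12-month scan gaps.
5. Optionally, add an interval-censored estimate as a sensitivity analysis. It is not a correction: in the cells above it lies below the truth while Kaplan-Meier lies above.

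Items 2 and 3 make the endpoint reproducible; they do not remove the scan-spacing shift.

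The cost is a wording amendment and a little more analysis, with no extra scans. Reported PFS may be slightly less favourable. A parametric sensitivity model would add a shape assumption. The case report form is not included in the documents, so whether it already records the date of the last negative assessment cannot be checked and should be confirmed.

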18.2 Sample Size/Accrual Rate

- Our study patient population comprise of the patients with stage III NSCLC who have activating EGFR mutation.
- Based on historical data, the mediastinal nodal clearance rate of 30% or higher will justify the further study of neoadjuvant erlotinib and the rate of 15% or less will be considered ineffective.
- An optimal two-stage phase II study⁴⁰ is designed to test the null hypothesis that the rate is 15% or less versus the alternative hypothesis that the response rate is at least 30%.
- The total sample size if the study will be 55 patients
- Nineteen (19) patients will be accrued in the first stage of phase II. **If 3 or fewer responses are observed during the first stage then the treatment will be concluded early for lack of efficacy.** Otherwise, 36 additional patients will be accrued for the second stage. **If 12 or fewer responses among 55 patients are observed by the end of this phase II study, no further investigation of this treatment regimen is warranted.**
- The power under this design is 80% and the type I error is 0.05. The probability of early stopping at the first stage is 68.4% if the true response rate is 15%. If the true response rate is 30%, the probability of early stopping at the first stage is 13.3%.
- By the end of this study, response rate will be estimated and its exact 95% confidence interval will be calculated. A total of 55 patients ensure that the 95% confidence interval for the estimated response rate will be within +/- 15.7%.
- The Montefiore Medical Center will initiate the study. Additional 4-5 sites will be subcontracted by Montefiore Medical Center to expedite accrual in the study.
- With the initial anticipated accrual of 1-2 patients per month across 4-5 centers, it will take approximately 12 months for the first stage of the study. The total accrual period is assumed to be approximately 24-36 months, with a follow-up period of an additional 12 months after the last patient is enrolled.

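### The final exact 95% interval takes no account of the two-stage design or the one-sided 5% test, so it includes the 15% rate at two positive results, 13/55 and 14/55

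*Combined protocol and SAP*

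**What the plan says.** Section 18.2 (Sample Size/Accrual Rate) describes an optimal two-stage design to "test the null hypothesis that the rate is 15% or less versus the alternative hypothesis that the response rate is at least 30" per cent. On the two rates it says that "the rate of 15% or less will be considered ineffective" and that "the mediastinal nodal clearance rate of 30% or higher will justify the further study of neoadjuvant erlotinib".

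- **First stage:** "Nineteen (19) patients will be accrued in the first stage of phase II", and "If 3 or fewer responses are observed during the first stage then the treatment will be concluded early for lack of efficacy". Otherwise 36 more patients are accrued.
- **Final rule:** "If 12 or fewer responses among 55 patients are observed by the end of this phase II study", the regimen is not taken further. A positive result is therefore 13 or more of 55.
- **Operating characteristics:** "The power under this design is 80% and the type I error is 0.05". Early stopping has probability 68.4% at a true 15% and 13.3% at a true 30%.
- **Estimation:** "By the end of this study, response rate will be estimated and its exact 95% confidence interval will be calculated".

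Section 18.1 (Study Design/Analytic Plan) adds that response rates are reported as proportions with 95% intervals. Neither section names an interval method or mentions the first-stage stop in connection with estimation. Neither uses the word one-sided, and neither says how to read a positive result whose interval contains 15%.

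**The concern.** The decision rule and the reported interval answer different questions in two ways.

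- **Method.** A single-sample interval treats the 55 patients as one fixed sample. Under the plan, samples with 3 or fewer successes in the first 19 never reach 55, so tail probabilities at 55 differ from the ordinary binomial ones.
- **Level.** A two-sided 95% interval puts 2.5% in each tail, whereas the test puts 5% in one tail.

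The primary objective is estimation of the clearance rate, so the interval will be printed beside the go/no-go conclusion. At the lowest positive counts the two would point in different directions, and the plan gives no rule for reading them together. The method and level could then be chosen after the count is known.

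**Working it through.** **Inputs, all from 18.2:** n1 = 19, stop at 3 or fewer; 36 further patients, total 55; positive at 13 or more; p0 = 15%, p1 = 30%.

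**1. Reproduce the design.** With X ~ Bin(19, p) and Y ~ Bin(36, p), define

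G_k(p) = Σ_{x=4..19} P(X = x) · P(Y ≥ k − x).

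- Type I error: G_13(0.15) = 0.0477, within the stated 0.05.
- Power: G_13(0.30) = 0.8006.
- Early stopping: P(X ≤ 3) = 0.684 at 15% and 0.133 at 30%.

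All agree with the plan. The 0.05 is a one-sided level, because only high counts reject 15%.

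**2. The interval as the plan reads.** The Clopper-Pearson lower limit solves P(Bin(55, p) ≥ k) = α/2, and the upper limit solves P(Bin(55, p) ≤ k) = α/2.

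**3. The two-stage exact interval (stage-wise ordering).** The lower limit solves G_k(p) = α/2 and the upper limit solves 1 − G_{k+1}(p) = α/2. For a trial stopped at 19, this ordering gives the ordinary Clopper-Pearson interval on x/19, so only results at 55 change.

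| Result | Rule | Single-sample 95% | Single-sample 90% | Two-stage 95% | Two-stage 90% |
|---|---|---|---|---|---|
| 12/55 (21.8%) | negative | 11.8–35.0% | 13.1–32.9% | 12.4–40.0% | 13.8–36.8% |
| 13/55 (23.6%) | positive | 13.2–37.0% | 14.6–34.9% | 13.7–40.5% | 15.1–37.7% |
| 14/55 (25.5%) | positive | 14.7–39.0% | 16.1–36.9% | 15.0–41.4% | 16.5–38.7% |
| 15/55 (27.3%) | positive | 16.1–41.0% | 17.6–38.8% | 16.4–42.5% | 17.9–40.1% |

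The tail probabilities at p = 15% show why:

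- At 13/55 the single-sample tail is 0.0603 (above 0.05) and the two-stage tail is 0.0477 (below it).
- At 14/55 the single-sample tail is 0.0297 (above 0.025) and the two-stage tail is 0.02496 (just below it). The two-stage 95% lower limit there is just above 15.0%.

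At 13/55, changing only the level leaves 14.6% as the lower limit, and changing only the method leaves 13.7%. Both changes are needed for interval and rule to agree at the boundary.

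**4. How often a positive result falls at 13 or 14.**

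- True 30%: 5.35% + 7.48% = 12.8% of trials; 12.83/80.06 = 16% of positive results.
- True 25%: 9.07% + 9.86% = 18.9%; 18.93/55.35 = 34%.
- True 15%: 2.27% + 1.31% = 3.6%; 3.58/4.77 = 75%.

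**5. Coverage of the single-sample 95% interval under the design** (x/19 if stopped, x/55 otherwise; true rates 10% to 60% in half-point steps). It runs from 94.3% (at 33.5%) to about 99%. It is below 95% only at 33.5% and from 40% to 42%, by at most 0.7 points. From 15% to 30% it is at or above 95%.

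**6. Direction of bias of the ordinary proportion.**

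| True rate | Bias over all trials (points) | Bias if 55 reached (points) | Mean estimate if positive |
|---|---|---|---|
| 15% | −2.0 | +3.4 | 25.4% |
| 20% | −2.4 | +2.3 | 26.7% |
| 25% | −2.1 | +1.5 | 28.7% |
| 30% | −1.4 | +0.9 | 31.7% |

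The uniformly minimum variance unbiased estimate (UMVUE) is 27.1% at 13/55, and the median-unbiased estimate is 24.1%. Among positive trials the UMVUE averages 29.2%, 30.7% and 33.1% at true rates of 20%, 25% and 30%. Each is further above the truth than the ordinary proportion.

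**The case against.** The best defence is that nothing is decided by the interval. Section 18.2 decides on a count, the count rule has its stated error rates, and no go/no-go outcome would change. That stands.

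A second defence is that a two-sided 95% interval beside a one-sided 5% test is stricter by construction, so overlap with 15% is not a logical contradiction. That also stands as far as level is concerned. It does not account for 13/55, where even the single-sample 90% interval includes 15% although the design rejects it.

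Third, the plan names no method, and exact could mean a two-stage interval. The plain proportions in 18.1 make the single-sample reading the natural one, but it is inferred from silence. On the other reading the mismatch disappears at 14/55 and remains at 13/55.

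Two stronger readings are tempting, and the documents do not support them:

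- **That the reported clearance rate will be understated.** The downward bias is an average over all trials, including those stopped at 19. In trials that reach 55 patients or end positive, the ordinary proportion is biased upward. Making the UMVUE the headline estimate would increase that upward shift.
- **That the interval seriously under-covers.** It is not exact under the design, but it is mostly conservative and the largest shortfall found is 0.7 points.

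**Conclusion.** The point holds as a minor one. The interval that 18.1 and 18.2 together imply does not account for the first-stage stop and is at a different level from the test. At 13/55 and 14/55 it includes the rate that the plan calls ineffective, although both counts are positive. The chance of such a result is 12.8% at a true 30% and 18.9% at a true 25%. The decision rule, its type I error and its power are sound. The ordinary proportion is an acceptable estimate if its bias is described with the right condition.

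This rests on three assumptions: that exact means the single-sample binomial interval; that the 0.05 is one-sided, as the form of the hypotheses implies; and that the stages contain exactly 19 and 55 analysed patients.

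**What to change.** In 18.2, state that the type I error of 0.05 is one-sided, and replace the interval sentence with wording such as:

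> The clearance rate will be estimated by the observed proportion. Its confidence interval will be the exact interval for the two-stage design under stage-wise ordering. The two-sided 90% interval (equivalently for the lower limit, a one-sided 95% bound) corresponds to the one-sided 5% decision. The two-stage 95% interval will also be shown; it is at a stricter level than the test and includes 15% at 13/55 (lower limit 13.7%).

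A design-adjusted estimate (median-unbiased or UMVUE) is optional. If used, one should be named in advance and labelled supplementary. The sentence on proportions and intervals in 18.1 should refer to 18.2 for the primary endpoint.

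The cost is a wording change, a few lines of code and one extra interval in the report. No patients or procedures are affected.

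### The ±15.7% precision stated for 55 patients is not what n = 55 gives: the ordinary exact 95% interval has a half-width of at most 13.8 points

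*Combined protocol and SAP*

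**What the plan says.** Section 18.1 makes estimation a primary statistical aim, namely "to obtain preliminary estimates of the rate of mediastinal nodal clearance and the rate of complete pathological response". It adds: "Response rates will be summarized by computing proportions and corresponding 95% confidence intervals".

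Section 18.2 gives the inputs for the precision statement:

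- Sample size: "The total sample size if the study will be 55 patients".
- Interval: "By the end of this study, response rate will be estimated and its exact 95% confidence interval will be calculated".
- Precision: "A total of 55 patients ensure that the 95% confidence interval for the estimated response rate will be within +/- 15.7" percent.

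The same list sets out the two-stage design. Nineteen patients enter stage 1, and the trial stops with 3 or fewer responses. Otherwise 36 more are accrued, and 12 or fewer responses in 55 is a negative result. On error rates it says: "The power under this design is 80% and the type I error is 0.05". No assumed rate, formula or adjustment for the interim look is given for the 15.7.

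**The concern.** The sample size, the confidence level and the word exact stand next to the 15.7, so a reader should be able to recompute it. A worst-case 95% half-width at n = 55 should be roughly 13 to 14 points, and 15.7 is what a noticeably smaller sample would give. The figure is quoted to one decimal and attributed to the 55 patients, so it reads as a calculated result.

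Little is at stake, but not nothing. This is the plan's only statement of how precisely the clearance rate will be estimated, and estimating that rate is a primary objective. A figure that cannot be traced to its own inputs also makes a reader doubt the neighbouring numbers, which are in fact sound.

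**Working it through.** **Inputs (section 18.2).** n = 55; 95% level; exact interval, taken as two-sided because no sidedness is stated; two-stage rule 3/19 then 12/55; null rate 15%, alternative 30%.

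**1. Trying to reproduce 15.7.** No standard 95% method tried gives it as a worst case at n = 55. It does match other inputs:

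- Normal approximation, 95%, rate 0.5, n = 39: 1.96 × 0.5/√39 = 15.69 points.
- Normal approximation, 98%, rate 0.5, n = 55: 2.326 × 0.5/√55 = 15.68 points.
- Clopper-Pearson, 95%: n of about 42 to 43 (maximum half-width 15.81 and 15.62).

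The documents do not confirm any of these as the source.

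**2. The ordinary exact interval at n = 55.** For x responses, the lower limit is the 0.025 quantile of Beta(x, 55 − x + 1) and the upper limit is the 0.975 quantile of Beta(x + 1, 55 − x). Over all x from 0 to 55:

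- The maximum half-width is at x = 27 (and, by symmetry, 28). At 27/55 = 49.1% the interval is 35.35% to 62.93%, so the half-width is (62.93 − 35.35)/2 = 13.79 points.
- The largest distance from the estimate to either limit is 14.09 points, at x = 22 (upper limit) and x = 33 (lower limit).

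At outcomes near the design rates the interval is narrower, as expected:

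| Responses | Estimate | 95% interval | Half-width |
|---|---|---|---|
| 8/55 | 14.5% | 6.5% to 26.7% | 10.1 |
| 16/55 | 29.1% | 17.6% to 42.9% | 12.6 |
| 17/55 | 30.9% | 19.1% to 44.8% | 12.8 |

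**3. Other 95% methods at n = 55, worst case.**

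- Normal approximation: 1.96 × √(0.25/55) = 13.2 points.
- With continuity correction: 13.21 + 100/(2 × 55) = 13.21 + 0.91 = 14.1 points.
- Wilson: 12.8 (13.6 with continuity correction). Agresti-Coull: 12.8.

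**4. An exact interval that allows for the interim look.** The plan does not mention one, but the design is two-stage, so it was checked. Outcomes are ordered by stage. The lower limit solves P(continue and X ≥ x) = 0.025, and the upper limit solves 1 − P(continue and X ≥ x + 1) = 0.025. X is the total of 19 + 36 patients, and continuing requires at least 4 responses in stage 1.

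| Responses | 95% interval | Half-width |
|---|---|---|
| 4/55 | 6.05% to 39.58% | 16.8 |
| 8/55 | 8.09% to 39.58% | 15.7 |
| 13/55 | 13.68% to 40.55% | 13.4 |

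The maximum is 16.8, so 15.7 is not the bound for this interval either.

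**5. The neighbouring figures.** Exact binomial sums for the rule 3/19, 12/55 give:

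- Early stopping at 15%: P(X ≤ 3 of 19) = 0.0456 + 0.1529 + 0.2428 + 0.2428 = 0.684. The plan states 68.4%.
- Early stopping at 30%: 0.133. The plan states 13.3%.
- Type I error 0.0477, within the stated 0.05. Power 0.8006, against the stated 80%.

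All of these reproduce. The precision figure is the exception.

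**The case against.** The strongest reply is that the sentence is literally true. It promises only that the interval stays within 15.7 points, and 13.8 (or 14.1 for the longer side) is within 15.7. The looseness is in the cautious direction, so no one is promised more precision than 55 patients deliver with the ordinary exact interval. That stands, and it limits the weight of the point. It does not make 15.7 the figure for n = 55.

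A second reply is that the text says only exact and does not name Clopper-Pearson, so an interval adjusted for the two-stage design may have been meant. The observation is fair, but it does not rescue the number. On that reading the half-width exceeds 15.7 at 4 to 8 of 55 and reaches 16.8, so the promise would be false and not merely loose. What remains of the reply is that any replacement bound must name its method.

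Third, comparing 15.7 with the 10.1 or 12.6 points found near the design rates is not like for like, because a bound over all outcomes is always wider than the interval at a low rate. That is right. The fair size of the discrepancy is the gap between the two worst cases. The narrower values show only what the trial is likely to report.

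**Conclusion.** The stated precision is wrong as the result of n = 55 at 95%. For the ordinary exact interval the worst-case half-width is 13.8 points, so the stated figure is 15.7 − 13.8 = 1.9 points too wide, or 15.7 − 14.1 = 1.6 points if the longer side is the measure. This rests on three assumptions: a two-sided interval, the unadjusted Clopper-Pearson method as the usual meaning of exact, and a trial that completes both stages with all 55 patients in the denominator. The origin of 15.7 cannot be established from the documents. Severity is minor: the figure feeds into no decision boundary, error rate or sample size, and the interval calculated from the data would be the same.

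**What to change.** In section 18.2, replace the precision sentence with: *With 55 patients the exact (Clopper-Pearson) two-sided 95% CI has a half-width of at most 13.8 percentage points (no limit more than 14.1 points from the estimate).* Keep the method name, since the bound does not hold for other exact intervals. If the sponsor intended a different interval, the sentence should name it and give that interval's own bound.

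Optionally, as clarification and not correction, add one sentence saying that the count rule (13 or more of 55) governs the decision and the 95% interval is descriptive. At 13/55 (13.2% to 37.0%) and 14/55 (14.7% to 39.0%) the rule is met although the Clopper-Pearson interval includes 15%.

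The cost is one sentence of wording, or two with the clarification. Patient numbers, boundaries, power, type I error and analysis are unchanged.
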